12.4 COLLECTION AND PROCESSING OF TUMOR SPECIMENS

1. Following resection, tumor specimens will be expeditiously transported to the pathology suite, where a pathologist will evaluate and identify the portion of the specimen in excess of that required for pathological analysis.
2. A small piece will be flash-frozen and transported to each institution's designated banking resource facility as is routinely performed for all head and neck cancer specimens.
3. Where tumor size and quality permit, the remainder of the specimen will be transported on ice to the designated laboratory for harvesting tumor-infiltrating lymphocytes (TIL) according to a standard protocol. Briefly, after removal of fat, blood and necrotic areas, tumor tissue will be washed in RPMI-1640 containing 50 µg/ml gentamycin, and cut into 1 mm 3 pieces in a petri dish covered with RPMI-1640. The sample is washed again with RPMI-1640 and upon transfer to flasks, dissociated using 0.05% collagenase type IV and 0.02% DNase type I in RPMI-1640 supplemented with 5% (v/v) fetal calf serum and antibiotics. Tissues will then be dissociated for up to 4 h using a magnetic stirrer at 37°C. The digest will then be passed through 90 µm and 50 µm nylon mesh to remove clumps, and the filtrate washed in 2–3 mL medium followed by centrifugation at 350 g for 10 min and resuspension in 2 mL medium.
4. PBMC will be washed, counted, aliquotted and frozen in DMSO-containing freezing medium prior to long-term storage in liquid nitrogen. All tubes will bear self-adhesive labels that clearly identify the trial code, the patient number, the patient initials, and the visit number. Sterile technique will be maintained throughout so that viable cells may be cultured and assayed after thawing.

12.5 IMMUNOPHENOTYPING AND CHARACTERIZATION OF HPV-SPECIFIC T CELL RESPONSES

1. Following purification from whole blood or tumor, mononuclear cells will be cultured 48 hours in the presence or absence of pools of 15-20-mer overlapping peptides encompassing the full-length HPV16 E6 and E7 antigens, or control (CMV, EBV and Flu virus) peptide mixtures.
2. After 48 hrs of stimulation, an aliquot of supernatant from the culture will be harvested and frozen at -80°C for future studies of cytokine production.
3. E6/E7-specific T cell responses will be determined by ELISPOT, flow-cytometry for intracellular IFN-γ staining, or other comparable method. In brief, staining for T cell surface markers (CD3, CD4, CD8) with labeled antibodies is performed prior to fixation/permeabilization of cells. Fix/permed cells are then stained with labeled antibody to IFN-γ, a marker of activated cytotoxic T cells. Multicolor flow cytometric analysis is then performed on an LSR II flow cytometer.
4. Additional flow cytometry staining panels to characterize NK cells (CD56), T cell activation and exhaustion markers (granzyme, perforin, CTLA-4, PD-1), regulatory T cell (CD127, CD25), and myeloid populations (CD11c, CD11b, CD33, HLA-DR) will be used to perform multi-dimensional immunophenotyping of effector and regulatory cell populations.

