6.0 RESEARCH PLAN AND METHODS

This is a window of opportunity single-arm phase II clinical trial in which a group of surgically-resectable HPVOPC patients will receive the ADXS11-001 vaccine before standard-of-care transoral surgical resection. Vaccinated patients will be enrolled according to a Simon's two-stage design, with an initial cohort of 9 patients enrolled before preliminary analysis, and a

subsequent cohort of 13 patients enrolled if statistical criteria are met. To better understand the immunology of un-vaccinated HPVOPC patients, we will also enroll an optional observational group of up to 10 patients with the same characteristics who will undergo transoral resection without vaccination. We will collect, process and store tumor specimens, tumor-derived leukocytes, and serum and cellular components of peripheral blood, at different time points from study patients prior to analysis of batched samples at a later date once the specimens from 5 or more patients are available.

6.1 SCHEME:

[figure not shown]

Figure 2. Flow diagram for clinical trial of ADXS11-001 therapeutic HPV vaccine in HPV+ OPC patients. OPSCC – oropharyngeal squamous cell carcinoma. XRT – radiation therapy.

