16.0 STATISTICAL CONSIDERATIONS

We will employ the Simon's two-stage design for the phase II clinical trials. (Simon R. Optimal two-stage designs for phase II clinical trials. *Control Clin Trials* 1989; 10: 1-10.) This trial design maximizes the chances of detecting a true difference in the HPV-specific T cell frequencies in pre- and post-vaccination samples while minimizing the number of patients treated if there is no difference. We plan to enroll and vaccinate up to 22 HPV+ OPC patients. In parallel we also plan to enroll and collect samples from up to 10 un-vaccinated HPVOPC patients in the observational group.

(a) Definition of primary outcome/endpoint:

We will determine the rate of vaccine-induced T cell responses at the time of surgical resection. For evaluation of immune responses in the peripheral blood, for each patient, a vaccine-induced T cell response will be considered:

1. Any post-vaccination E6- or E7-specific T cell response frequency (response to E6 or E7 peptide pool, minus nonspecific background, measured by ELISPOT or intracellular cytokine staining) equal or greater to two times the initial pre-vaccination baseline response. Where two baseline measurements are available, the mean value will be used.
2. When pre-vaccination E6/E7-specific T cell responses are not observed, any post-vaccination response at least two-fold greater than the average value of nonspecific background (for ELISPOT, approx. 10-15 spots/well) will be considered a positive response.

Toxicity will be scored using the NCI CTCAE 4.0 criteria, with any grade 3 or 4 toxicity considered as an adverse outcome.

(b) Definition of secondary outcomes/endpoints:

1. We will determine the rate of vaccine-induced T cell responses at various time-points after surgery (3W, 6W, 3M, 6M, 12M). Otherwise as per the primary outcome/endpoint

(c) Analytic plan for primary objective:

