For each patient, the baseline mean frequency +/- SD of peptide-specific IFN- γ and/or TNF α expressing T cells in the peripheral blood will be determined by averaging the results of 3 replicate assays. At each subsequent blood draw, the mean frequency +/- SD of IFN- γ positive T cells will be determined in an identical fashion, and vaccine-induced T cell responses determined as described above. The response to each peptide will be evaluated separately. While the ADXS 11-001 vaccine contains the HPV E7 protein, cross-reactive responses to E6 and other HPV proteins can be observed following vaccination (personal communication, [name], Advaxis Pharmaceuticals) so we will monitor responses to E6, E7 and E2 peptides.

The trial is designed to conclude that ADXS 11-001 vaccination is likely highly immunogenic and worth further investigation if the overall rate of vaccine-induced T cell responses is 75% or more. ADXS 11-001 vaccination will be deemed not worthy of further investigation if the overall rate of vaccine-induced T cell responses is less than 50%.

For this trial, we propose a maximum sample size of 22 subjects, with 9 eligible subjects accrued in the first stage and 13 eligible subjects accrued in the second stage. One interim monitoring will be performed at the end of the first stage. The trial will be terminated early if it is evident that the T cell response rate is lower than the acceptable level. Since we do not yet know when the peak effect of vaccination will be, we will consider any responses at time of surgery or at 3 or 6 weeks after surgery to "count" as positive vaccine-induced T cell responses. If responses in five (5) or fewer patients are observed during the first stage, we will conclude that ADXS 11-001 vaccination does not merit continued investigation due to lack of immunologic efficacy. Otherwise accrual will continue until a total of 22 evaluable patients have been vaccinated and assessed for T cell response and toxicity.

If after completion of accrual more than fourteen (14/22) patients have vaccine-induced T cell responses, we will conclude that ADXS 11-001 vaccination is sufficiently active to justify recommendation for future studies.

(d) Analytic plan for secondary objectives:

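### The two-fold responder rule cannot separate an HPV-specific rise from one shared by all recall responses, and the control-peptide cultures that could show the difference enter no rule

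*Combined protocol and SAP*

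**What the plan says.** Section 12.5, item 1, sets up 48-hour cultures with or without E6/E7 peptide pools, "or control (CMV, EBV and Flu virus) peptide mixtures". The documents do not mention the controls again. Item 3 leaves the platform open: ELISPOT, intracellular staining or a comparable method.

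Section 16.0(a) defines a response as the "response to E6 or E7 peptide pool, minus nonspecific background, measured by ELISPOT or intracellular cytokine staining", at a level "equal or greater to two times the initial pre-vaccination baseline response". For patients with no baseline response, the second rule accepts "any post-vaccination response at least two-fold greater than the average value of nonspecific background". Two safeguards are given: "Where two baseline measurements are available, the mean value will be used", and each frequency comes from "averaging the results of 3 replicate assays". Section 16.0(c) counts a response at surgery, 3 weeks or 6 weeks.

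Section 6.0 stores samples "prior to analysis of batched samples at a later date once the specimens from 5 or more patients are available". Section 8.6 says the design rests on pre/post comparison within patients, not on vaccinated versus unvaccinated results.

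**The concern.** The hypothesis concerns antigen-specific T cells, and the decision rests on a within-patient ratio in a single arm. Background subtraction deals with spots or cells that appear without peptide. It does not deal with a factor that multiplies every peptide response in a sample: thaw quality, reagent lot or run, or general T-cell activation after a live bacterial vector or surgery. Averaging two baselines steadies the denominator. Three replicates reduce well-to-well error. Neither touches a factor carried by the post-vaccination sample itself.

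Unrelated recall antigens are the natural within-sample check: if CMV and EBV responses double along with E7, the doubling is not evidence of HPV specificity. The plan sets up those cultures and then gives them no role, so a doubling from either cause is scored as vaccine-induced.

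**Working it through.** **1. The plan's own design figures.** Section 16.0(c) gives 9 then 13 patients, a stop at 5 or fewer responders, and success above 14 of 22. With scored response rate q and success cut-off c,

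P(go) = Σ over x = 6 to 9 of Bin(x; 9, q) × P(Bin(13, q) ≥ c − x).

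- c = 15 (as worded): 5.25% at q = 0.50, 75.6% at q = 0.75.
- c = 14: 9.70% and 80.69%, which match the stated 10% and 80.7%.
- Early stopping at q = 0.50 is 74.6%, and expected N is 9 + 0.254 × 13 = 12.3, for either cut-off. These agree with the stated 75% and 13 after rounding.

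The cut-off wording and the stated error rates differ by one patient. That is a separate matter, so both cut-offs are carried below.

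**2. How often the rule is met with no vaccine effect.** The documents give no assay variability, so this is an illustration. Assumptions: response at a draw = shared sample factor × antigen factor, both lognormal with σ = √ln(1 + CV²); baseline = mean of two draws; E6 or E7 at three draws; first response rule only. The control requirement adds that the E6/E7 fold change is at least twice the same sample's control fold change. The control is given the same residual CV as the antigens.

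| Shared CV | Residual CV | Plan's rule, any of 3 draws | Plan's rule plus control requirement |
|---|---|---|---|
| 30% | 20% | 19% | 3% |
| 30% | 30% | 30% | 12% |
| 50% | 20% | 35% | 4% |
| 50% | 30% | 42% | 14% |

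At surgery alone, with residual CV 20%, the plan's rule gives 8% (shared CV 30%) and 16% (shared CV 50%).

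Hand check for E7 at surgery, CVs 30% and 20%: the variance of the log ratio is about 1.5 × (0.0862 + 0.0392) = 0.188, SD 0.434. P(Z > 0.693/0.434 = 1.60) is about 5.5%, against 4.8% simulated. The simulated value is a little lower because an arithmetic mean of baselines exceeds the geometric mean.

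Replacing the two-fold test by the ratio alone, with the control averaged over three mixtures, gives 3.6% to 21.7% over the same four settings. Dividing adds the control's own noise, so requiring both conditions works better.

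**3. Effect on the go decision.** If a share f of true non-responders is misscored, q = p + (1 − p)f.

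| True rate p | f | q | P(go), above 14/22 | P(go), 14/22 or more |
|---|---|---|---|---|
| 50% | 0 | 0.50 | 5.2% | 9.7% |
| 50% | 10% | 0.55 | 12.1% | 19.4% |
| 50% | 20% | 0.60 | 23.7% | 33.3% |
| 40% | 20% | 0.52 | 7.5% | 13.1% |
| 0 | 35% | 0.35 | 0.1% | 0.4% |
| 0 | 42% | 0.42 | 0.9% | 2.2% |

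**4. What the control requirement costs.** With shared CV 30%, residual CV 20% and a true two-fold rise in E7 only, detection over three draws falls from 77% to 58%; at surgery alone, from 48% to 30%. For a true 2.5-fold rise over three draws it falls from 91% to 84%.

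**The case against.** The strongest reply is that the design tests against 50%, not zero, so assay noise does not make an inert vaccine look active. That stands: the last two rows of step 3 are close to zero. A reader might infer that general activation alone could carry the trial. If every recall response rose 1.5-fold (shared CV 30%, residual CV 20%), 62% of patients would be scored over three draws and P(go) would be about 30% or 40%. But the documents give no figure for such a shift. Section 3.2 speaks of innate stimulation without a size for recall responses.

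It can also be said that the 50% reference is itself a scored rate, so the stated error rates hold by definition. On that reading the error rate is intact, but a scored 50% is then not an HPV-specific 50%, and the specificity gap remains.

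Other points stand in part:

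- Section 6.0 does not say that a patient's tubes will be split between runs; it is silent. The gap is the missing requirement.
- Intracellular staining reports a fraction of T cells, so cell recovery largely cancels there. It matters more for ELISPOT, and the platform is not fixed.
- Section 12.5 says the control cultures are set up, not that they are read at every draw.
- Section 14.0 allows injected influenza vaccine during the trial, so the influenza control can move for an unrelated reason. If the control rose 1.5-fold (assumed), detection of a true 2.5-fold HPV rise over three draws would fall from 91% to 50%.
- Unvaccinated patients give draws 1, 4, 5 and 6, which could show drift from runs or surgery. That group is optional, at most 10, and enters no decision rule. It cannot show activation by the vector.
- A laboratory manual might hold acceptance rules, but the documents cite none.

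These limit how the control should be used. They do not supply a rule that uses it.

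**Conclusion.** The point holds as a gap in specificity. The responder rule removes additive background but not a proportional change common to all recall responses, the control cultures enter no rule, and one patient's compared draws need not share a run.

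Under assumed shared CVs of 30-50% and residual CVs of 20-30%, about 19-42% of unaffected patients would be scored over the three counted draws, against about 3-14% with the control requirement. The decision is affected when the true rate is near the 50% reference: 10% misscoring roughly doubles P(go) under either cut-off and takes it above the stated 10%. The documents do not support the stronger claim that an inert vaccine would probably pass. All the false-responder rates depend on the assumed CVs, and the second response rule was not modelled.

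This is a worthwhile, inexpensive improvement to what the trial can conclude about HPV specificity. It does not call for replacing the primary rule.

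**What to change.** **Sections 6.0 and 12.5.** Require that all of a patient's draws entering one comparison (1, 2, 4, 5 and 6) are assayed in a single run on one platform. State that the control wells are read at each of these draws.

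**Section 16.0.** Keep the primary rule and its Simon boundaries. Prespecify a supporting sensitivity analysis in which a patient counts if the primary rule is met and the same antigen's fold change, divided by that sample's control-peptide fold change, is also at least two. Report this rate with a confidence interval and do not test it against the stage boundaries, which were set for the unadjusted rate. Further:

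- Read the three control mixtures separately where possible, and state in advance how they are combined. Leave influenza out of the control for patients given influenza vaccine between compared draws.
- Patients judged under the second rule have no baseline E6/E7 response and so no ratio. Report the control fold change beside their result.
- Report patients with no measurable control response unadjusted, and give their number.

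**Cost.** Plan wording and batch planning, with no new blood draws. Control wells must be read at each compared draw, which Section 12.5 implies but does not state; if that was not intended, it is added assay work. Single-run assay means waiting for the 6-week draw, which Section 16.0(c) already needs before a patient can be called a non-responder. The adjusted rate is less sensitive to true rises near two-fold (77% to 58% in the setting above), and some patients cannot be adjusted. That is why it should support the primary analysis and not replace it.

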12.6 IMMUNOHISTOCHEMISTRY (IHC) AND MOLECULAR PROFILING OF TUMOR SPECIMENS

1. Tumor specimens obtained during standard-of-care resection will be harvested for preparation of tissue microarrays (TMA) from formalin-fixed, paraffin-embedded (FFPE) tissue specimens, according to each site's routine protocols. Histological slides which include tumor tissue and surrounding normal tissue from the tumor margin will be created with the help of the designated pathology facility at each site.

2. Histological slides will be subjected to immunofluorescent staining and analysis. These data are quantified using image analysis instrumentation and software. This approach has allowed successful characterization and quantification of up to 5-7 antigens in single sections⁵⁴.

3. We will utilize a comprehensive panel of IHC markers including markers for myeloid cells; Treg (CD4/FOXP3); NK cells (CD56); and CD3+, CD4+ and CD8+ T cells. Staining for these markers will be examined by multiplex immunofluorescence and their density in tumor quantitated by digital image analysis. Tumor infiltrating myeloid cells will be identified with the markers CD33 (myeloid-derived suppressor cells, MDSC), CD11b (MDSC, some macrophages, some DCs), and CD68 (macrophages), and neutrophils (CD66b).

4. A portion of the tumor specimen will be flash frozen according to each site's routine protocols, and cryopreserved for future molecular biology analyses of immune and cancer-related gene expression.

13.0 CRITERIA FOR REMOVAL FROM STUDY

Subjects may withdraw consent at any time for any reason or be discontinued from the trial at the discretion of the investigator, should any untoward effect occur. In addition, a subject may be withdrawn by the investigator or the sponsor/Study Chair if enrollment into the trial is inappropriate, the trial plan is violated, or for administrative and/or other safety reasons.

Patients will be removed from the study, and notified of this fact, under the following circumstances:

1. Failure to obtain at least one baseline blood draw.
2. Failure to receive at least one vaccination (if in vaccine arm).
3. The patient experiences a grade IV toxicity.

If a patient is removed from the study or if the patient wishes to discontinue participation before all visits and monitoring are complete, the following will occur:

- **For patients in the treatment group, 3 years of *Lm* surveillance monitoring will be offered.**
- **Patients in the treatment group will be provided with sufficient antibiotics to complete the 6 months of post-vaccine treatment as described above.**

14.0 Concurrent Therapies and Procedures

All prescription and nonprescription medication (excluding vitamins, nutritional supplements and hormone replacement therapy) taken by the subject from 30 days prior to screening and up to and including completion of the 3-year *Lm* surveillance period will be recorded in the medical record and on the eCRF. Any addition, deletion, or change in the dose of these medications will also be recorded. Generic names should be used to eliminate confusion that may result from trade names. Protocol-mandated prophylactic medications, antibiotics and procedures administered/performed following the completion of study treatment, including during the 3-year *Lm* surveillance period, should also be captured in the eCRF.

Study subjects should be reminded that acetaminophen should not be used for pretreatment prophylaxis associated with the foreseeable AEs related to the study treatment since this medication can interfere with treatment.

Medications specifically prohibited in the exclusion criteria are not allowed during the ongoing trial. If there is a clinical indication for one of these or other medications specifically prohibited during the trial, discontinuation from trial therapy may be required. The Investigator should discuss any questions regarding this with the Sponsor. The final decision on any supportive therapy rests with the Investigator and/or the subject's primary physician. However, the decision to continue the subject's on-trial therapy requires the mutual agreement of the Investigator, the Sponsor, and the subject.

Subjects are prohibited from receiving the following therapies during the screening and treatment phases (including retreatment for post-complete response relapse) of this trial:

- Anti-cancer systemic chemotherapy or biological therapy
- Surgical treatment as per consultation with the sponsor
- PI3K and TNF α inhibitors
- Immunotherapy not specified in this protocol
- Investigational agents other than ADXS11-001
- Radiation therapy (except palliative radiation therapy for disease-related pain with a consult with the sponsor's medical monitor)
- Live vaccines within 30 days prior to the first dose of trial treatment and while participating in the trial. Examples of live vaccines include, but are not limited to, the following: measles, mumps, rubella, chicken pox, yellow fever, rabies, BCG, and typhoid (oral) vaccine. Seasonal influenza vaccines for injection are generally killed virus vaccines and are allowed; however, intranasal influenza vaccines (e.g., Flu-Mist®) are live attenuated vaccines and are not allowed.
- Acetaminophen is not to be used for premedication but may be used for supportive care measures. NSAIDs, such as naproxen and ibuprofen have been evaluated and are confirmed not to interfere with efficacy.

Subjects who, in the assessment by the Investigator, require the use of any of the aforementioned treatments for clinical management should be removed from the trial. Subjects may receive other medications that the Investigator deems to be medically necessary.

15 Treatment Discontinuation:

Surveillance monitoring for the detection of *Lm* will be initiated at the completion of study treatment according to the protocol or at the time of study discontinuation if earlier. This surveillance monitoring phase will consist of a 6 month course of oral antibiotics, obtaining a blood sample to monitor CBC, CMP, including CRP and ESR, and blood cultures at regular intervals. This testing will be performed on all subjects who have received at least one dose of ADXS11-001. It will occur at 3 months(+/- 3 weeks), 6 months(+/- 3 weeks), 9 months(+/- 1 Month), 12 months(+/- 1 Month), and every 4 months(+/- 1 Month) for 2nd and 3rd year beginning after the last dose of study treatment. If a persistent increase in CRP and/or ESR is observed with negative blood cultures for *Listeria* during this time the subject should be evaluated and treated, as appropriate, for another possible cause. In the event that a definite cause has not been identified then subjects must continue to be monitored closely, including another additional testing and a blood culture, for possible signs/symptoms of listeriosis. This testing may be performed at the investigative site or at another acceptable location following consultation with the Sponsor.

